The study site will be the Dell Children's Medical Center Emergency Department, an urban pediatric ED with approximately 80,000 visits per year, of which than 3000 visits are due to asthma related issues. The patient population will include children with previously diagnosed asthma, aged ≥ 6 years to < 18 years old, presenting to our pediatric ED with breathing difficulty or cough, and found to have an initial FEV₁ less than 70% predicted based on NHANES III study data (moderate to severe exacerbation).^{2,15,23} Patients will be excluded from the study if they have no clinical evidence of exacerbation by asthma scoring (PAS score of 0), have preexisting chronic lung disease besides asthma, have congenital heart disease, have neuromuscular disease, have a suspected intrathoracic foreign body, have an allergy or other contraindication to a study medication, or have severe breathing difficulty requiring immediate resuscitation.

Subject Eligibility:

Inclusion:

1. Age \geq 6 years and $<$ 18 years
2. History of physician diagnosed asthma
3. Presenting to ED with acute asthma exacerbation
4. Parent or guardian speaks English or Spanish.

Exclusion:

1. PAS score of 0
2. Initial FEV₁ greater than 70% predicted
3. Patient unable to perform acceptable initial spirometry
4. Pregnancy or breast-feeding
5. Immediate resuscitation required
6. Chronic lung disease (other than asthma)
7. Congenital heart disease
8. Neuromuscular disease
9. Suspected intrathoracic foreign body
10. Allergy or other contraindication to study medication

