Subjects will be identified in triage and will be screened and enrolled by a member of the study team (P1). A research nurse will be available for 6-8 hours per day to serve as the primary enrolling personnel during these hours. Additionally, each of the pediatric emergency medicine fellows and several pediatric emergency medicine attending physicians will be trained and certified for enrollment, and will enroll subjects during evenings, nights, and weekends. We anticipate having study personnel available at a minimum of 18 hours per day for enrollment. The P1 personnel will assess the potential subject and screen potential subjects for inclusion and exclusion criteria as detailed above. As a part of screening, the P1 personnel will perform baseline spirometry measurements prior to consent. Spirometry is a minimal risk procedure that is performed as standard of care in many emergency departments nationwide (either as spirometry, or PEF measurements). Performing spirometry prior to consent will expedite screening, and for children who have FEV₁ greater than 70% predicted or those unable to perform acceptable spirometry, this will allow them to be excluded and their asthma treated more promptly. This will avoid excluded children having to undergo consent prior to being excluded and receiving treatment for their acute asthma. Consent will be obtained from the parent or guardian of all patients, and assent obtained from patients who are at least 7 years of age. If required prior to study enrollment, supplemental oxygen may be administered to maintain oxygen saturation $>$ 90% if there is evidence of hypoxemia on continuous pulse-oximetry. If there is a delay of greater than 15 minutes due to the consent process, a unit dose (2.5mg) of albuterol may be given with a standard t-piece nebulizer up to 3 times as needed. Patients requiring this unit dose of albuterol will still be eligible for enrollment so long as they meet enrollment criteria following this therapy. Following consent, the P1 personnel will record an initial set of vital signs (temperature, heart rate, respiratory rate, blood pressure, and peripheral pulse oximetry), and record baseline asthma scores using multiple previously validated asthma severity scores (PAS and PASS).^{24,25} At this point, study patients will be randomized to receive treatment with either the experimental (breath-enhanced) or control (t-piece) nebulizer. Randomization will be performed with a computerized randomization process. Pre-assigned opaque envelopes will be used in order to conceal randomized assignments, preventing any knowledge of patient assignment to the enrolling personnel. A second

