
member of the study team (P2) will open the subject's randomized folder that will dictate the appropriate therapy arm. P2 will administer a single 5mg dose of albuterol via the appropriate nebulizer as determined by randomization. P1 will be blinded to the treatment arm, whereas P2 will not be blinded. Following 15 minutes of therapy - sufficient time for both treatment arms to be complete - P1 will perform a post-treatment assessment of the subject including a repeat set of vital signs, pulse-oximetry, asthma scoring, and spirometry measurements.

Patients randomized to the "control" arm will receive therapy with our standard ED nebulizer, the Hudson RCI® Micro Mist® nebulizer (Teleflex Medical®, Research Triangle Park, NJ). The treatment will be preferentially administered with a mouthpiece. Patients unable or unwilling to use a mouthpiece (as determined by the P2) will receive therapy with a simple mask (Hudson RCI®, Teleflex Medical®, Research Triangle Park, NJ).

Patients randomized to the "experimental" arm will receive therapy with a NebuTech® HDN®, Breath-Enhanced High Density Jet Nebulizer (Salter Labs®, Arvin, CA). Treatments will be preferentially administered with a mouthpiece. Patients unable or unwilling to use a mouthpiece (as determined by the P2) will receive therapy with a mask. The NebuTech® HDN® allows for a proprietary vented mask, which still utilizes the breath-enhanced features of the system (I-Guard™ Valved Aerosol Delivery System, Salter Labs®, Arvin, CA).

Spirometry measurements will be taken using a handheld spirometer which has been validated in healthy controls (NDD EasyOne®).²⁶ In keeping with the most recent American Thoracic Society guidelines, participants will be asked to perform a minimum of 3 and maximum of 8 forced expiratory maneuvers in order to obtain 3 adequate samples as determined by the device.²⁷ Based on prior data, more than 8 attempts at spirometry may result in patient fatigue which will artificially decrease the patient's performance on lung function testing²⁷. The highest recorded FEV₁ will be used for analysis. Flow-volume loops will be evaluated by a pulmonologist in order to assess adequacy of spirometry measurements for all patients, and those with inadequate loops will be excluded from FEV₁ analysis. The pulmonologist involved will be blinded to therapy arm.

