Treatment groups will be analyzed on an intention-to-treat basis. The primary outcome for this study is change in FEV₁ from initial presentation to reassessment. By evaluating data from previously performed studies,^{16,18} we have conducted a sample size calculation using an estimated baseline initial FEV₁ of 55% predicted, and an estimated 10% FEV₁ improvement with standard of care. The calculations were performed using STATA 13 statistical software (StataCorp, LP, College Station, TX). In order to detect an improvement differential of 5% (absolute) between treatment arms, with a power of 0.80 and alpha of 0.05, we will need 64 patients enrolled in each arm. It has been shown previously that as few as 35%-65% of patients with severe asthma exacerbations are able to successfully perform peak expiratory flow or spirometry.^{22,28} However other studies have not had significant difficulty with pediatric subjects performing spirometry.¹⁵ Several of these studies evaluated patients as young as 5 years old. Due to the inconsistency of data, and the fact that we will be enrolling patients 6 years and older, we estimate that with sufficient coaching, approximately 60% of patients in this study will be able to successfully complete interpretable spirometry. Based on this, we will need to enroll 213 patients in order to obtain interpretable data on 128 patients. We will perform ongoing flow-volume loop analysis of obtained data in order to adjust our total enrollment goal based on the percentage of subjects with interpretable data sets.

Statistical Analysis

The primary outcome of change in FEV₁ will be compared between the two groups using a two-tailed t-test, or non-parametric equivalent if the data is non-normally distributed. Baseline group characteristics will be summarized in a table with means and standard deviations for continuous data, percentages for categorical data, and medians with interquartile ranges for ordinal data.

Secondary outcomes for this study will include hospital admission rates, emergency department (ED) length of stay (LOS), changes in asthma severity scores, vital sign changes, medication side effects, and total quantity of albuterol given in the ED. Analysis of these variables will be completed using appropriate statistical analysis depending on the nature of the data (t-test for continuous, chi square of Fisher's exact test for categorical, and Mann-Whitney U test for ordinal). Non-parametric tests will be used when appropriate.

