Finally, if significant baseline differences in the groups occur, linear multivariable regression analysis of the primary endpoint will be performed to adjust for potential confounders.

VII. Human Subject Interactions

a. Sources of Potential Participants

Subjects will be screened for enrolment if they present to the DCMC ED with signs of an acute asthma exacerbation. The nursing staff at triage, as well as Pediatric Emergency Medicine study personnel will identify potential research subjects. In addition, a full time research RN will be available to assist with identification and enrollment of potential subjects, if funding allows as mentioned above. Subjects that meet all inclusion and exclusion criteria and consent to participate will be enrolled.

b. Procedure for Recruitment of Participants

All patients who have physician-diagnosed asthma will be triaged upon arrival to the emergency department, and will be evaluated by a triage nurse. Upon identification of a patient with previously diagnosed asthma who is presenting with breathing difficulty or cough, the triage nurse will contact study personnel, either in the form of the research nurse (if available) or other study personnel who are available within the ED. Additionally, research personnel may identify subjects through periodic monitoring of the ED tracking board from the research office. Study personnel will approach the parent or guardian for potential study enrollment. As a part of screening for inclusion and exclusion criteria, study personnel will briefly explain the nature of the research project and perform baseline spirometry measurement prior to obtaining informed consent. Performance of this minimal risk study is considered by many to be standard of care in acute asthma, and will expedite screening of patients if performed prior to consent.

c. Procedure of Obtaining Informed Consent

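### Is the enrolment target of 213 wrong because children who cannot do spirometry are already excluded before consent?

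*Combined protocol and SAP*

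**What the plan says.** The Sample Size section (part VI) asks for 64 patients per arm to detect a 5-point difference in FEV₁ improvement, with power 0.80 and alpha 0.05. It then allows for unusable spirometry. It reports that "as few as 35%-65% of patients with severe asthma exacerbations are able to successfully perform peak expiratory flow or spirometry", notes that other studies had little difficulty, and settles on an estimate that "approximately 60% of patients in this study will be able to successfully complete interpretable spirometry". From this it concludes that "we will need to enroll 213 patients in order to obtain interpretable data on 128 patients". The same paragraph ends with a commitment to review loops during the trial and "adjust our total enrollment goal based on the percentage of subjects with interpretable data sets".

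Under Subject Eligibility, exclusion 3 is "Patient unable to perform acceptable initial spirometry". The design text in part VI explains why the test comes before consent: for "those unable to perform acceptable spirometry, this will allow them to be excluded and their asthma treated more promptly". Section VII.b repeats that staff will "perform baseline spirometry measurement prior to obtaining informed consent".

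A second check comes later. The design text says that "Flow-volume loops will be evaluated by a pulmonologist in order to assess adequacy of spirometry measurements for all patients". Patients with inadequate loops leave the FEV₁ analysis, and the pulmonologist does not know the treatment arm.

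The Data and safety Monitoring text (part VIII) schedules one interim comparison of adverse event and admission rates at the study midpoint, given as subject #107. Adverse events are also reviewed within 24 hours of occurrence.

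**The concern.** An inflation factor should describe losses among the people being counted. Here the people counted are enrolled children, and each of them has already produced acceptable baseline spirometry at the bedside. The published figures behind the 60% describe a hurdle that these children have cleared. On that reading, about 213 is the number to test at screening to find 128 who can perform, and the number to enrol should be smaller.

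If so, the trial would randomise more acutely ill children than it needs. The review at #107, set as half of 213, would also come later than halfway. Neither effect would reduce power or raise the type I error. The stakes are the surplus patients and the timing of one safety look.

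**Working it through.** **Inputs from the documents.** Difference 5 points, power 0.80, alpha 0.05 two-sided, 64 per arm, usable rate 60%, target 213, midpoint review at #107. The SD of the change is not stated.

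**Reproducing the plan's figures.**
- With an assumed SD of 10, the standardised difference is 5/10 = 0.5. The two-sample t-test then needs 63.8 per arm, so 64, and 128 in total. Power at 64 per arm is 0.801.
- 128/0.60 = 213.3, stated as 213.
- 213/2 = 106.5, stated as #107.

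The arithmetic is sound. The only question is which rate belongs in the denominator.

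**If the usable rate among enrolled children differs from 60%.** The documents give no other rate, so a range on both sides is assumed. Enrolment needed is 128/r, rounded up. Power assumes SD 10 and that all 213 are enrolled.

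| Usable rate r | Enrolment needed | 213 minus need | Power at 213 | 107 / need |
|---|---|---|---|---|
| 50% | 256 | −43 | 0.72 | 42% |
| 60% | 213 | 0 | 0.80 | 50% |
| 70% | 183 | 30 | 0.86 | 58% |
| 80% | 160 | 53 | 0.90 | 67% |
| 90% | 143 | 70 | 0.93 | 75% |
| 95% | 135 | 78 | 0.94 | 79% |

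**What 60% means per session.** The outcome is a change, so the baseline and post-treatment loops must both survive review. Suppose each is usable independently with the same probability p, so that r = p².
- Break-even: p = √0.60 = 0.775. At about 77% per session, 213 is right.
- Above it: p = 0.85, 0.90, 0.95 gives r = 0.7225, 0.81, 0.9025 and enrolment of 178, 159, 142.
- Below it: p = 0.75, 0.70 gives r = 0.5625, 0.49 and enrolment of 228, 262.

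Nothing in the documents says on which side of 77% these children fall. Passing at the bedside and passing the pulmonologist's review are separate steps, and the post-treatment session has not taken place when a child is enrolled.

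**What the adjustment rule does.** Replacing 60% by the observed percentage turns the target into 128 divided by that percentage, which is the calculation the concern asks for. There is time to apply it: even if every enrolled child were usable, 128 would be needed, so the goal can still be reset at 107 enrolled. By then the standard error of the observed rate is √(0.6 × 0.4/107) = 0.047 at a true 60%, or √(0.8 × 0.2/107) = 0.039 at a true 80%. That is precise enough to tell the two apart.

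**Where #107 falls.** With 128 needed at the lowest, #107 comes no later than 107/128 = 84% of enrolment. With 262 needed, it comes at 107/262 = 41%. The review takes place before enrolment ends in every case.

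**The case for a change.** The best case for a change is this. All the evidence offered for 60% concerns ability to perform the test. If 60% is the share of all presenting children who would give interpretable data, then removing those who fail at baseline can only raise the rate among the rest, and 213 is an upper bound. A loss of 40% among children who have just passed bedside testing has no cited support. The adjustment rule gives no timing or threshold, and nothing says that #107 moves when the goal moves.

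Part of this stands. The 60% is thinly justified as a rate among enrolled children, and the text on #107 is silent about a revised goal.

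The upper-bound argument depends on its opening condition, and the plan's wording points the other way: the 60% is stated for patients in the study and for interpretable data, which is the right quantity to divide by. The cited ability figures then serve as background to an investigator's estimate. Whether those studies counted one session or two, or judged loops at the bedside or afterwards, cannot be seen from the documents. A lower target set in advance would need a post-enrolment rate that the documents do not give, so 70%, 80% or 90% would be no better founded than 60%. It would also exchange a margin for a risk of too few usable patients.

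On #107, the review is described as the midpoint, with the subject number in parentheses. Staff who revise the goal can reasonably read the number as following from it.

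**Conclusion.** No change is needed. The reasoning behind the 60% is weaker than it should be, because it cites a hurdle that enrolled children have already cleared. The documents do not show whether 213 is too high or too low: under the two-session model, needed enrolment runs from 142 at 95% per session to 262 at 70%, with 213 right at about 77%. The excesses of 30 to 78 patients at usable rates of 70% to 95% arise only if all 213 are enrolled and the plan's own adjustment rule is ignored. Followed as written, the plan replaces the guess with the observed percentage. That percentage concerns whether loops can be read, and the pulmonologist who judges them is blinded to arm, so the adjustment has no bearing on alpha. The review at #107 may come somewhat before or after halfway, but it precedes the end of enrolment, and adverse events are reviewed within 24 hours regardless.

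The power figures rest on the assumed SD of 10. The per-session figures rest on independence and equal rates across the two sessions. The conclusion rests on neither. It rests on the adjustment rule being applied and on the missing post-enrolment loss rate.

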A member of the research team will collect baseline data from the subject's guardian. Data will be recorded on a standardized form and will include subject demographics (including age, ethnicity, primary care provider), baseline home therapies, and assessment of baseline asthma severity, nature and duration of current symptoms, and treatments prior to ED arrival. Following the post-treatment assessment, the P1 (blinded) study personnel will be asked to predict which nebulizer was utilized in the study, in order to evaluate adequacy of blinding.

Following completion of the experimental stage as detailed above, patients will be released to receive standard of care therapy as determined by the assigned attending ED physician. We anticipate that the majority of patients will receive care according to the DCMC ED asthma pathway, including administration of inhaled ipratropium bromide and an oral systemic glucocorticoid. However, some patients may be treated off of the ED pathway, and variability in subsequent therapy is possible. Data will be recorded on a standardized form

regarding subsequent therapy through the remainder of the patients' ED course. Patients who are admitted to the hospital will be treated according to the standard of care as determined by the inpatient attending physician. Following disposition from the ED, no further data will be obtained from patients.

Sample Size

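### The primary t-test on change in FEV₁ fixes the baseline slope at 1 and leaves further adjustment to an undefined trigger; one pre-specified ANCOVA on baseline FEV₁ would gain precision and clarity at almost no cost

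*Combined protocol and SAP*

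**What the plan says.** Section VI, Sample Size, defines the endpoint: "The primary outcome for this study is change in FEV₁ from initial presentation to reassessment". Section VI, Statistical Analysis, gives the test: "The primary outcome of change in FEV₁ will be compared between the two groups using a two-tailed t-test, or non-parametric equivalent". The non-parametric alternative applies "if the data is non-normally distributed", and no criterion is given for that judgement.

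The same section ends by saying that "if significant baseline differences in the groups occur, linear multivariable regression analysis of the primary endpoint will be performed to adjust for potential confounders". It does not state:
- a test or threshold for significance;
- which baseline variables are examined;
- which covariates are entered;
- whether the regression replaces the t-test or supports it.

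Baseline FEV₁ is not named as a covariate anywhere. It is nonetheless available for every eligible child. Section VI states that "the P1 personnel will perform baseline spirometry measurements prior to consent", with randomisation after consent, and eligibility requires that the child is "found to have an initial FEV₁ less than 70% predicted".

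**The concern.** A t-test on post-treatment minus baseline FEV₁ is a baseline-adjusted comparison with the slope fixed at 1. ANCOVA estimates that slope from the data. If the true slope is not 1, the fixed-slope test has a larger residual variance, and part of any chance imbalance in baseline FEV₁ stays in the estimate.

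The conditional regression does not repair this. A trigger at p < 0.05 on baseline FEV₁ would fire in about 5% of randomised trials, so the gain is forgone in the other 95%.

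The open wording also leaves two choices until the data are seen: t-test or rank test, and unadjusted or adjusted. At stake are some precision and the certainty of having one named primary result. The trial expects only 60% of enrolled children to give interpretable spirometry, so each evaluable child costs about 1/0.60 = 1.7 enrolments.

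**Working it through.** **Inputs from Section VI, Sample Size.** Difference 5 points ("In order to detect an improvement differential of 5% (absolute) between treatment arms"), power 0.80, alpha 0.05, 64 per arm, 60% interpretable, 213 enrolled.

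**Assumptions.** The documents give no SD of change, baseline SD or slope. The slope b is varied from 1 to 0.4 and the baseline SD over 5, 7 and 10 points of % predicted.

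**1. Reproducing the plan's figures.** The 64 cannot be derived from the stated inputs alone. In the two-sample noncentral-t calculation (two-sided 0.05, difference 5), an SD of change of 10 requires 63.8, so 64 per arm; SDs from 9.94 to 10.01 all give 64. Power at 64 per arm and SD 10 is 0.801. Enrolment reproduces: 128/0.60 = 213.3.

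**2. ANCOVA power at 64 per arm.** With SD of change 10, residual variance = 100 − (1 − b)² × SD_b². For b = 0.6 this is 100 − 0.16 × 25 = 96, 100 − 0.16 × 49 = 92.16 and 100 − 0.16 × 100 = 84.

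| Baseline SD | b = 1 | b = 0.8 | b = 0.6 | b = 0.4 |
|---|---|---|---|---|
| 5 | 0.801 | 0.805 | 0.817 | 0.837 |
| 7 | 0.801 | 0.809 | 0.832 | 0.871 |
| 10 | 0.801 | 0.817 | 0.865 | 0.939 |

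These values leave out the cost of estimating the slope. At b = 1 that cost multiplies the variance by about 1 + 1/124 and takes power from 0.801 to 0.798. In simulation (40,000 trials per setting), ANCOVA with HC2 standard errors came within 0.01 of the formula values.

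**3. The same gain as sample size, at b = 0.6.**
- To match ANCOVA's precision at 64 per arm, the t-test needs 64 × 100/(96, 92.16, 84) = 66.7, 69.4, 76.2, so 67, 70 or 77 per arm.
- Enrolment is then 134/0.60, 140/0.60 and 154/0.60 = 223, 233 or 257, against 213.
- Equivalently, for the planned power of 0.80, ANCOVA needs about 62, 59 or 54 per arm instead of 64.

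**4. Chance imbalance left in the t-test, at b = 0.6.** The shift in the estimate has size (1 − b) × imbalance.
- Median imbalance, 0.674 × SD_b × √(2/64): 0.60, 0.83, 1.19. Shift 0.24, 0.33, 0.48 points; conditional type I error 0.045, 0.043, 0.038.
- Largest imbalance that escapes adjustment, if significance is read as p < 0.05 (an assumption): 1.75, 2.45, 3.50. Shift 0.70, 0.98, 1.40 points; conditional type I error 0.061, 0.073, 0.099.

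**5. What the trigger recovers.** Simulation with 64 per arm, baseline SD 10, 40,000 trials, and adjustment only if baseline FEV₁ differs at p < 0.05. The last column is type I error under the null if whichever of the two tests is significant were reported.

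| Slope | t-test power | ANCOVA power | Trigger rule power | Type I error, either test |
|---|---|---|---|---|
| 0.5 | 80.4% | 89.9% | 81.5% | 7.2% |
| 0.7 | 80.2% | 83.5% | 80.5% | 6.4% |
| 0.85 | 80.2% | 80.7% | 80.2% | 5.8% |
| 1 | 80.7% | 80.4% | 80.6% | 5.4% |

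Under the null at b = 0.6, type I error is 0.048 to 0.052 for the t-test, 0.049 to 0.052 for ANCOVA with HC2, and 0.046 to 0.049 for the trigger rule applied as a fixed procedure.

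**The case against.** The change-score t-test is a legitimate primary analysis, named in advance. It is unbiased, holds its alpha and has the planned power if the SD is 10. All of that stands, and it is why this is an improvement and not an error.

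The gain rests on values the documents do not supply, and it can be very small. At slope 0.9 power is 0.802, 0.803 or 0.805 against 0.801. Slope 0.6 implies pre-post correlations of only 0.29, 0.40 or 0.55, for readings taken shortly before and after one 15-minute treatment. Excluding children above 70% predicted narrows the baseline spread and can shrink the gain further. These points limit the size. The low correlations, however, come partly from the assumed SDs: with SD of change 10 and baseline SD 5, even slope 1 gives 5/√(25 + 100) = 0.45.

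The enrolment figures of 223 to 257 describe matching a power that the plan does not target; 213 suffices for 0.80 under the assumed SD. The conditional errors of 6% to 10% are a worst case at the edge of an assumed threshold. Both are fair qualifications.

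The regression can be read as an added analysis, since the t-test is the one named for the primary outcome. That is the more natural reading, but the plan does not say so. The 5.4% to 7.2% range shows what the open wording permits; it does not suggest that anyone intends to use it that way.

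Finally, ANCOVA needs a defined baseline. Section VI allows albuterol before randomisation when consent is delayed, with eligibility judged after it, while the endpoint is measured from initial presentation. This ambiguity is real, but it affects the planned change score equally.

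**Conclusion.** The concern holds as a recommended improvement in precision and pre-specification, not as a validity error. Overall type I error stays near 5% for any one rule fixed in advance, and planned power is kept if the SD of change is about 10.

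Under that back-solved SD, ANCOVA raises power from 0.80 to between 0.81 and 0.94 for slopes of 0.8 to 0.4 and baseline SDs of 5 to 10. It gives no gain at slope 1. Gains towards the lower end are quite possible, given the ceiling on baseline FEV₁ and the short interval between readings. Confidence in the size is medium, because the documents give no SD, slope or correlation. The missing definitions of the trigger, the covariates, the regression's role and the normality criterion are plain from the text and need no assumption.

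**What to change.** **Core change, in Section VI, Statistical Analysis.** Make the single primary analysis an ANCOVA of post-treatment FEV₁ (% predicted) on arm and baseline FEV₁ (% predicted). Report the adjusted mean difference with its 95% CI and HC2 robust standard errors, whatever the baseline comparisons or normality checks show. Delete the trigger based on significant baseline differences. Keep the t-test and the rank test as supportive analyses.

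**Define the terms.** State the FEV₁ scale: the sample size uses % predicted, but the analysis sentence names no unit. State which reading is the baseline, and reconcile the passage on albuterol during consent delays with the endpoint's starting point at initial presentation.

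**Optional additions, separable from the core.** Add pre-randomisation ED albuterol as a covariate only if it is confirmed to be recorded for each child. The data-collection text lists "treatments prior to ED arrival" and subsequent therapy. The secondary outcome of total ED albuterol suggests that the quantity may be captured, but its timing is not stated. Adjust changes in vital signs and asthma scores for their baselines where the scale allows.

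**Cost.** The core change is to analysis wording, plus the clarification of which reading is baseline; no new measurement is needed. If the slope is in fact 1, the loss is about 0.003 of power with ordinary or HC2 standard errors, and about 0.01 with HC3. The albuterol covariate needs a check of the data form.
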